### **C. Evaluation after treatment**

Evaluation of curative effects and safety is conducted at the end of the drug therapy, six and twelve months after the treatment. Its content is the same as pre-trial evaluation.

## **VII. Records and reports of adverse events**

### **A. Adverse events**

The term of adverse events encompass any signs, symptoms, syndromes or diseases affecting health condition of subjects during the trial. The term also includes clinically relevant conditions found by laboratory test or other diagnostic procedures. It may call for unplanned treatment, or lead to withdrawal from the trial. Adverse events may be: new disease; deterioration of symptoms accompanying disease progression during treatment; certain events not related to the trial; combination of one or more events above.

#### **Serious adverse events**

At any dose of the test drug or at any time during the observation period, the following adverse events occurs: death; immediate life-threatening events; requirement of hospitalization or prolonged hospital stay; disability; congenital malformations; other events with important medical implications (those do not immediately endanger life or cause death or require hospitalization, but may harm the patient or require interventions to prevent one of the consequences defined above) and requiring medical treatment to prevent permanent injury.

#### **B. Adverse reactions**

Harmful and unexpected reactions caused by pharmaceutical applications under normal use of drugs and prescribed doses.

#### **C. Degree of adverse reactions:**

- 1) Mild: causing mild discomfort which can be tolerated and does not affect daily life; under this circumstance, the subject does not need to discontinue medication.
- 2) Moderate: causing discomfort which affects patients' daily life.
- 3) Severe: affecting daily life; cannot be endured by the subject or cause organ damage and need to withdraw medication.
- 4) Very serious: risk of disability or death; require emergent rescue and drug withdraw.

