## **VI. Follow-up plan and content**

### **A. Evaluation before the trial**

Each subject should complete the following items in four weeks before the treatment:

- 1) Complete medical history
- 2) Detailed personal profile
- 3) VAS pain score
- 4) Quality of Life (Qol) Rating Scale
- 5) Frequency of blood transfusion therapy
- 6) A physical examination
- 7) Blood and urine routine examination
- 8) Liver and kidney function, blood lipid test
- 9) Coagulation I+D dimer examination
- 10) abdominal and pelvic cavity contrast-enhanced CT + small intestine reconstruction CT examination (for patients with gastrointestinal system affected)
- 11) Digestive system endoscopy (for patients with gastrointestinal system affected)
- 12) Ultrasound, MRI examination of the lesion
- 13) (Female of childbearing age) blood/urine pregnancy test

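### The only severity scale (VII.C) has no laboratory criterion, so a symptom-free laboratory adverse event short of organ damage or risk of disability or death fits no grade and cannot be ranked by size

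*Combined protocol and SAP*

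**What the plan says.** Section VII.C (Degree of adverse reactions) sets four grades:

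- Mild: "causing mild discomfort which can be tolerated and does not affect daily life". The entry adds that the subject need not stop the drug.
- Moderate: "causing discomfort which affects patients' daily life".
- Severe: an effect on daily life, followed by "cannot be endured by the subject or cause organ damage and need to withdraw medication".
- Very serious: "risk of disability or death; require emergent rescue and drug withdraw".

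No grade refers to a laboratory value, and no external toxicity scale is cited anywhere in the document.

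Laboratory findings are nevertheless adverse events. Of that term, section VII.A says: "The term also includes clinically relevant conditions found by laboratory test or other diagnostic procedures". The Record and report section lists laboratory tests among the things to watch and has each event's extent entered in the case report form. Section VII.E(4) has its own follow-up rule for adverse events with abnormal laboratory values.

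The values are collected. Section VI.A includes "Blood and urine routine examination" and "Liver and kidney function, blood lipid test" before treatment. Sections VI.B and VI.C repeat the same content at months 3 and 6, at the end of therapy, and six and twelve months afterwards.

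**The concern.** The protocol admits laboratory abnormalities as adverse events and asks for the extent of each one, but its scale is built on how the patient feels and functions. Changes in liver enzymes, creatinine, lipids or blood counts can be substantial without symptoms. For such an event the investigator has no written basis for choosing a grade, and two investigators can grade the same value differently while both follow the protocol.

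Safety is objective 1, in a single-arm trial with a minimum of 20 patients. With no control group and few patients, a reader would use a severity summary to judge how well the drug was tolerated. For laboratory toxicity that summary would partly reflect individual improvisation.

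**Working it through.** No sample size, power or rate enters this point, so the check is to take one class of event through each grade. The event is a laboratory abnormality recorded as an adverse event under VII.A that causes no discomfort, leaves daily life unaffected, and falls short of organ damage and of any risk of disability or death.

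1. **Mild.** The definition requires mild discomfort. The event causes none, so strictly it does not qualify. It does meet the other two conditions (tolerated, daily life unaffected), which makes Mild the nearest fit and the probable default.
2. **Moderate.** The definition requires discomfort that affects daily life. The event has neither, so it can never be Moderate, whatever the laboratory value.
3. **Severe.** The route that does not depend on what the patient can endure is organ damage with a need to withdraw the drug. No laboratory value is tied to organ damage, so whether a given rise crosses that line is a matter of opinion. The entry also opens with an effect on daily life. If that is a joint condition, even symptom-free organ damage misses Severe; if it is an alternative, such damage qualifies. The text allows both readings.
4. **Very serious.** This needs a risk of disability or death with emergency rescue. It does not depend on symptoms, but the event falls short of it by construction.

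Result: the event has no defined grade. A larger abnormality changes nothing until someone judges it to be organ damage or a threat of disability or death, and then it enters at Severe or Very serious. Size below that point is not represented.

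**Baseline.** Section IV.A(4) admits AST and ALT up to 2.5 x ULN. Take two patients who both show 2.5 x ULN on treatment, one who entered at 2.5 x ULN and one who entered at 1 x ULN. Relative to baseline the changes are 2.5/2.5 = 1.0-fold and 2.5/1 = 2.5-fold. A scale in multiples of ULN alone would treat them alike, so laboratory grading here needs a reference to the patient's own baseline.

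**Size.** The documents give no adverse event rates and no grade distribution, so the number of affected events cannot be derived. What can be stated is the leverage of one patient: at the minimum of 20, one patient moved between grades changes a percentage by 1/20 = 5 points, and by less if more are enrolled.

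**The case against.** The strongest reply is that this is a missing definition with no effect on a named analysis. The sections on relationship to the drug and on recording promise the incidence of adverse reactions and adverse events, and VIII.B promises an assessment of events and of their relationship to the drug. None of these depends on grade, and no tabulation by severity is specified. That stands. A reader might infer that a planned severity table understates toxicity. The documents name no such table, and the direction of any error is not shown; what they do plan is to record extent, and any later summary of it inherits the problem.

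A reader might also infer that VII.C grades by discomfort and daily life alone, so that a laboratory toxicity is Mild however large it is. The text does not support this. Severe includes organ damage, Very serious includes risk of disability or death, and Mild itself requires discomfort. Mild is a likely default, not an assigned grade.

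It can further be said that patients are protected whatever the grade. VII.E(1) requires abnormal laboratory tests to be taken seriously and immediate protective measures; VII.E(4) requires follow-up to baseline; the definition of serious events covers medically important events without requiring symptoms; IV.C(4) allows exit when continuing may be harmful. That also stands, and it answers any suggestion that the Mild wording by itself plays down action on a laboratory finding. It does not supply a grade.

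**Conclusion.** The point holds as a gap in a stated rule. VII.C cannot rank laboratory adverse events by size: a symptom-free one short of organ damage or risk of disability or death strictly fits no grade, is never Moderate, and is likely to be graded inconsistently or to default to Mild. Any summary of recorded severity would be unreliable for laboratory toxicity.

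The conclusion rests on the wording of VII.C and on VII.A counting laboratory findings as events. The default to Mild is a judgement about how investigators will behave; the document does not state it. The size is unknown because no rates are given, and the planned incidence figures are unaffected. This is a cheap improvement.

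**What to change.** - Keep VII.C for symptomatic events.
- Grade laboratory adverse events separately, on a standard published toxicity scale or in numeric bands in multiples of ULN (the unit IV.A(4) already uses). Reference the grade to the patient's baseline, because entry allows raised AST and ALT.
- In VIII.B, report the worst post-baseline grade per patient per test alongside the incidence already promised.
- Reconcile the wording on stopping the drug inside the VII.C grades with the exit criteria in IV.C and the tolerability provisions in V.C. For events that cannot be tolerated, V.C provides for stepwise dose reduction, while the Severe entry speaks of withdrawing the drug. No clinical rule is proposed here.

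The cost is one added table in the protocol and matching fields in the case report form; the laboratory tests are already scheduled. The downside is that severity counts may look less favourable.

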#### **D. Evaluation of the relationship between adverse reactions and experimental drug**

According to the 5-level judgment system, the relationships can be divided into 5 types: definitely related, very likely related, may be related, may be irrelevant, and definitely irrelevant. The first three are counted as adverse reactions, in which case the incidence of adverse reactions and adverse events should be reported.

#### **D. Record and report**

The investigator should explain to the patient or his/her legal guardian that it is required to truthfully reflect the changes in the condition after administration. Doctors should avoid suggestive questions. While observing the efficacy, pay close attention to the observation of adverse events or unanticipated side effects (including symptoms, signs, laboratory tests), analyze the causes, make judgments, and report the incidence of adverse reactions and adverse events.

For adverse events occurring during the trial, time, symptoms, extent, duration, treatment measures, outcomes, and some other items should be recorded in the case report form to evaluate the correlation with the test drug. Investigator should record it in detail, and then signs and dates.

## **E. Treatment of adverse events**

### 1) reporting system

Any adverse events, such as subjective discomfort and abnormal laboratory tests, should be taken seriously and carefully analyzed. Immediate measures should be taken to protect safety of the subject.

### 2) treatment procedure

Physicians are pre-trained to prevent certain types of adverse events or reactions that may occur in the study, so as to protect safety of patients. Treatment procedure of adverse event should be recorded in detail. Persistence and disappearance of adverse events should also be recorded.

### 3) treatment of serious adverse events

On the occurrence of any serious adverse event, research physician should report to primary PI within 24 hours, in addition to emergency treatment.

### 4) follow-up of unresolved adverse events

All adverse events should be tracked until they are properly resolved. Adverse events with abnormal laboratory values should be tracked until the value returns to baseline.

## **VIII. Statistical analysis**

Statistical analysis will be conducted by SPSS.

### **A. Methods of statistical analysis**

The categorical variables will be described by frequency distribution (number of cases and percentage). Continuous variables will be described with mean, median, minimum, maximum, first and third quartile. The confidence interval of all parameters is set to be 95%. All analyses will be conducted with SPSS.

### **B. Contents of statistical analysis**

- 1) General data analysis: Demographic variables and baseline characteristics will be summarized comprehensively by mean of descriptive statistics and/or appropriate frequency tables.
- 2) Evaluation of efficacy: According to follow-up and reexamination results, the patients' quality of life, size and volume of the lesions, tumor load control and improvement of symptoms will be analyzed.
- 3) Analysis of adverse events: Side effects and adverse events during medication will be assessed.
- 4) Evaluation of the relationship between adverse events and the tested drug

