## II. Objective

1. To evaluate the safety of sirolimus in treatment of blue rubber blisters syndrome (BRBNS), hereditary cutaneous and mucosal venous malformation (VMCM), and sporadic multiple VM.
2. To evaluate the efficacy of sirolimus in treatment of blue rubber blisters syndrome (BRBNS), hereditary cutaneous and mucosal venous malformation (VMCM), and sporadic multiple VM.

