### **III. Research Design**

1. This study is a prospective, nonrandomized, open-label, single-arm clinical trial. The sirolimus capsule (Rapamycin, Yixinke®), 0.5 mg/grain\*20/box, is produced by North China Pharmaceutical Co., Ltd.
2. All patients who meet inclusion criteria and sign informed consents receive sirolimus treatment for at least 6 months. Patients are followed up in a regular schedule.
3. No less than 20 patients should be enrolled.

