### **IV. Selection of subjects**

#### **A. Inclusion criteria**

- (1) Patients diagnosed with BRBNS, VMCM, sporadic multiple VM, or large single VM;
- (2) Age and gender are not limited;
- (3) Physical status ECOG 0~3;
- (4) Organ function is good, biochemical examination meets the following conditions:
  - a) AST  $\leq 2.5 \times$  upper limit of normal value (ULN),
  - b) ALT  $\leq 2.5 \times$  upper limit of normal value (ULN),
  - c) serum total bilirubin  $\leq 1.5 \times$  upper limit of normal value (ULN),
  - d) creatinine  $\leq 1.5 \times$  upper limit of normal (ULN);
- (5) Patients volunteer to participate in the trial. Participant or his/her legal guardian signs the informed consent form.

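### Large single VM is eligible but in neither objective, and Section VIII sets no paired change from baseline that accounts for rejected and withdrawn patients

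*Combined protocol and SAP*

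**What the plan says.** **Who is studied.** Section IV.A, criterion (1), admits four diagnoses: "Patients diagnosed with BRBNS, VMCM, sporadic multiple VM, or large single VM". Section II has two objectives. One begins "To evaluate the safety of sirolimus in treatment of blue rubber blisters syndrome (BRBNS" and the other "To evaluate the efficacy of sirolimus in treatment of blue rubber blisters syndrome (BRBNS". Both end with "hereditary cutaneous and mucosal venous malformation (VMCM), and sporadic multiple VM". Neither names large single VM.

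**Design and visits.** Section III(1) states: "This study is a prospective, nonrandomized, open-label, single-arm clinical trial". Section III also sets treatment of at least 6 months and a minimum of 20 patients. Section VI.B repeats the baseline examinations at months 3 and 6. Section VI.C adds evaluations at the end of therapy and 6 and 12 months after treatment.

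**Analysis.** Section VIII.A says: "Continuous variables will be described with mean, median, minimum, maximum, first and third quartile". It adds: "The confidence interval of all parameters is set to be 95" (per cent). Section VIII.B(2) gives the efficacy content: "According to follow-up and reexamination results, the patients' quality of life, size and volume of the lesions, tumor load control and improvement of symptoms". Section VIII does not mention diagnosis groups, change from baseline, a main visit, an analysis set or missing values.

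**Who may leave.** Section IV.C(3) withdraws patients for reasons that include compliance, safety and VM surgery. Section IV.D rejects protocol violators (1) and patients with incomplete or poor data (2). For adults, Section V.C(1) withdraws those who cannot tolerate the minimum dose. Section V.C(2) lets those without obvious improvement at month 3 withdraw if they cannot tolerate the changed dose. None of these sections says how such patients count in the results.

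**The concern.** There are two problems, and both concern which patients the reported result describes.

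First, Section II asks about three diagnoses and Section IV.A enrols four. Section VIII neither restricts the analysis to the three nor shows the fourth separately. A pooled safety or efficacy result would then answer a question that differs from the one in Section II, and a reader could not tell by how much.

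Second, in a single-arm trial each patient's own baseline is the only internal comparator. Summarising each variable visit by visit does not estimate within-patient change. It also allows the baseline summary to come from everyone and the month-6 summary only from those who stayed. Several of the exit routes are plausibly linked to doing badly, and Section V.C(2) is open only to adults who were not clearly improving. If these patients drop out of the month-6 summary unrecorded, the remaining group can look improved for that reason alone.

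**Working it through.** **1. Is there a figure to reproduce?** No. The minimum of 20 patients is given without an effect size, SD, power or dropout rate. The figures below show scale under stated assumptions. They are not corrections of a number in the plan.

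**2. Diagnoses side by side.**
- Section IV.A(1): BRBNS, VMCM, sporadic multiple VM, large single VM.
- Section II, safety: BRBNS, VMCM, sporadic multiple VM.
- Section II, efficacy: the same three.
- Section VIII: all patients, no split.

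The expected case mix is not given, so no size can be put on this mismatch.

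**3. Why separate visit summaries are not enough.** Let r be the correlation between a patient's baseline and month-6 values, and let the two SDs be equal. The standard error of the paired mean change is then sqrt(1 − r) times the one obtained by treating the visits as independent groups. For assumed r of 0.3, 0.5, 0.7 and 0.9 the factor is 0.84, 0.71, 0.55 and 0.32. Summaries by visit do not report r, so the interval for change cannot be recovered from them.

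**4. Precision of a paired result.** The 95% half-width, in SDs of the change, is t(0.975, n − 1)/sqrt(n).
- n = 20 (the stated minimum): 0.47
- n = 16 (4 set apart or missing): 0.53
- n = 12 (8 set apart or missing): 0.64
- n = 5 (an assumed large single VM group): 1.24

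A separate group of about 5 could only be described.

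**5. Selective loss (assumed).** Simulation of 200,000 trials of 20 patients, with change distributed N(0,1), so no drug effect. The m patients lowest on a variable that has correlation rho with the change are removed. Mean change in those who remain:
- m = 2: 0.183 at rho = 1, 0.091 at rho = 0.5, 0.000 at rho = 0
- m = 4: 0.332 at rho = 1, 0.166 at rho = 0.5, 0.000 at rho = 0

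The rho = 1 values are upper bounds, because they assume that exactly the worst patients are lost. As a check, the shift should scale with rho: 0.5 × 0.332 = 0.166.

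**6. Which patients have an on-treatment value?** The first scheduled efficacy evaluation on treatment is month 3 (Section VI.B). A patient who leaves before then has none, unless the end-of-therapy evaluation in Section VI.C is made at stopping. That section does not say whether it applies after withdrawal.

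**The case against.** **The mismatch may be only a slip.** Section XIII refers to BRBNS, VMCM and VM without the word multiple, and the background discusses single-lesion VM on the same pathway. The baseline frequency tables in Section VIII.B(1) could also show the case mix. This is a fair reading and supports adding the diagnosis to Section II. It does not remove the need to reconcile the two sections, and a baseline table does not separate the results.

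**Change is implied.** Section VI.B lists hemoglobin change, the examinations match baseline, and Section IX promises unified efficacy criteria. That is true, but Section VIII sets no analysis of change and Section IX gives no content.

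**The plan is descriptive.** This stands in one respect. A reader might infer that several measures and visits inflate the false-positive rate. The documents do not support attaching a rate to that, because the plan states no test and no success rule. A descriptive estimate still needs a defined quantity, visit and set of patients. The absence of a lead measure is therefore a secondary point here.

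**Loss need not favour the drug.** This also stands in part. Section V.C(1) removes adults for intolerance whatever their response, and Section V.C(2) applies to adults only. A reader might infer that the month-6 result will be biased. The documents show only that it can be, since they give no expected losses and do not say that rejection under Section IV.D means removal from the analysis.

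**MRI may not be done in everyone.** A reader might infer this, but Section VI.A asks each subject to complete the list, and the ultrasound and MRI item carries no restriction. Its stated coverage equals that of VAS and quality of life.

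**Conclusion.** The concern holds in this form. Eligibility and objectives disagree on large single VM, and Section VIII neither separates that group nor sets a paired change that accounts for everyone treated. Both can be settled in wording before analysis, and neither undermines the design.

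The eligibility mismatch has no stated size, because case mix is unknown. The possible shift from selective loss is 0.09 to 0.33 SD of the change for 2 to 4 of 20 patients lost, and 0 if loss is unrelated to change. Those figures rest wholly on the assumed number lost and the assumed correlation of 0.5 to 1. It would be too strong to say that the trial's result is biased, or that large single VM makes up a material share of patients. The documents give no data for either statement.

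**What to change.** (a) Reconcile Sections II and IV.A. Either add large single VM to both objectives, or report safety and efficacy for the three named diagnoses as the main result, with large single VM shown separately and descriptively.

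(b) In Section VIII, analyse each continuous efficacy measure in Sections VI.B and VIII.B as paired change from baseline to month 6 with a 95% CI. Treat the month-3, end-of-therapy and post-treatment evaluations as supportive. Treatment lasts at least 6 months, so the end of therapy may fall at different times in different patients, whereas month 6 is fixed.

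(c) State in Section IV.D that rejected or withdrawn patients who took sirolimus stay in the safety analysis and in the efficacy accounting. Report the number with both values and the reason for each missing value. Add a sensitivity analysis using the last available on-treatment value (month 3, or an end-of-therapy evaluation made at stopping). Count patients with no on-treatment efficacy value as missing and report them. The last-value analysis makes its own assumption and is a check, not the main result.

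(d) As a secondary step, name before analysis one lead measure that is planned for every subject. MRI lesion volume is a candidate but needs target lesions fixed at baseline, for which Section VI.A gives no rule. VAS and quality of life are self-reported in an open-label trial with no age limit.

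**Cost.** Wording in Sections II, IV.D and VIII, with no new visits, tests or patients. If large single VM is set apart, the main result may rest on fewer than 20 patients, with the loss of precision shown in step 4 of the working.

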### **B. Evaluation during sirolimus treatment**

Adverse reactions are evaluated weekly during the first month of drug treatment. The efficacy and safety are then evaluated at the 3rd and 6th months, and the content of the examination is the same as the pre-trial evaluation.

- 1) Efficacy assessment:
  - a. Clinical symptom assessment (including VAS pain score, gastrointestinal bleeding, quality of life (Qol) evaluation, frequency of blood transfusion treatment and other related symptoms);
  - b. Changes in hemoglobin;
  - c. Coagulation I+D-dimer examination;
  - d. Nutritional status (including albumin, etc.);
  - e. Ultrasound, MRI examination of the lesion, abdominal and pelvic cavity contrast-enhanced CT + small intestine reconstruction CT examination, digestive system endoscopy to measure the size, quantity and total load of VM lesions;
- 2) Safety assessment: Safety parameters (such as asking adverse events, measuring laboratory values, vital signs, gastrointestinal bleeding, etc.) will be closely monitored on a regular basis throughout the study.
- 3) Treatment compliance: In order to monitor compliance, subjects are required to complete an electronic diary during the entire study period. Dates of drug intake will be tracked by this diary. At every visit, the investigator and the subject will review the electronic diary data together.

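### Section VIII.B item 3 confines the adverse-event analysis to the medication period, while the rest of the protocol evaluates, records and reports safety to 12 months after treatment

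*Combined protocol and SAP*

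**What the plan says.** Safety is Objective 1 (Section II). The analysis list in Section VIII.B covers adverse events in two items. Item 3 reads "Side effects and adverse events during medication will be assessed". Item 4 concerns the relationship of events to the drug and states no period.

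The other sections use a longer window:

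- Section VI.C: "Evaluation of curative effects and safety is conducted at the end of the drug therapy, six and twelve months after the treatment". The content of these visits matches the pre-trial evaluation.
- Section VII.A, on adverse events: "The term of adverse events encompass any signs, symptoms, syndromes or diseases affecting health condition of subjects during the trial".
- Section VII.A, on serious adverse events: "At any dose of the test drug or at any time during the observation period, the following adverse events occurs".
- Section VII, on relationship to the drug: "the incidence of adverse reactions and adverse events should be reported". No period is attached. The section on recording and reporting repeats the requirement, and has events across the trial entered in the case report form with their time, duration and outcome.

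On laboratory values, the pre-trial list in Section VI.A includes "Liver and kidney function, blood lipid test" as well as routine blood and urine tests, repeated at months 3 and 6 and at the Section VI.C visits. Section VI.B names them among the safety parameters: "measuring laboratory values, vital signs, gastrointestinal bleeding, etc.) will be closely monitored on a regular basis throughout the study". The general rule in Section VIII.A is: "Continuous variables will be described with mean, median, minimum, maximum, first and third quartile". It does not mention change from baseline. The one laboratory change named in the protocol is haemoglobin, listed under efficacy in Section VI.B.

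**The concern.** This is a conflict between stated rules rather than a missing detail. An event that begins after the last dose is an adverse event under Section VII and belongs in reported incidence there, yet it lies outside the period that item 3 sets for analysis. Two analysts working from different sections could report different event counts for the first-listed objective. The events at risk are late effects and those linked to stopping the drug, which the post-treatment visits are placed to detect.

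A smaller matter is attached. In a single-arm trial each patient's own baseline is the only laboratory comparator. Section IV.A admits patients with AST and ALT up to 2.5 x ULN and bilirubin and creatinine up to 1.5 x ULN, so a raised on-treatment value may have been present at entry. Section VIII lists no within-patient change for the laboratory safety values.

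**Working it through.** The plan gives no figure to reproduce here. The main check sets the sections side by side for one illustrative event: onset four months after the last dose.

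| Place | Period stated | Treatment of the event |
|---|---|---|
| VI.C | End of therapy, then 6 and 12 months after | Falls before the first post-treatment visit, where safety is evaluated |
| VII.A, adverse events | The trial | Is an adverse event |
| VII.A, serious adverse events | The observation period | Counts, if serious |
| VII, recording and reporting | The trial | Recorded; incidence reported |
| VII, relationship to drug | None | Incidence reported |
| VIII.B item 4 | None | Relationship to drug can be evaluated |
| VIII.B item 3 | Medication only | Not covered |

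Only item 3 leaves the event out, and no other section reconciles the two windows.

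**Length of the uncovered period.** Section III sets treatment at 6 months or more. I read the 6 and 12 months in Section VI.C as counted from the end of therapy, as its heading suggests. With T months of treatment, the share of follow-up time after medication is 12/(T + 12):

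- T = 6 (the minimum): 12/18 = 67%
- T = 12 (assumed): 12/24 = 50%
- T = 24 (assumed): 12/36 = 33%

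These are shares of calendar time. The documents give no event rates on or off the drug, so they do not convert to a number of events omitted.

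**Laboratory values, in three steps.**

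1. What is already covered. Section VII.A counts clinically relevant laboratory findings as adverse events. The recording section includes laboratory tests among what is observed and reported. Section VII.E 1) names abnormal laboratory tests as adverse events to be analysed carefully, and VII.E 4) follows laboratory events back to baseline. Haemoglobin, D-dimer and albumin are efficacy assessments in Section VI.B. The general rule in Section VIII.A would plausibly give summaries at each visit.
2. What is left: the within-patient change in liver, kidney, lipid and other blood-count values that nobody recorded as an event. Suppose one patient enters with AST at 2.5 x ULN and stays there, while another enters at 1 x ULN and rises to 2.5 x ULN. Their on-treatment values are identical, but their changes are 0 and 2.5 - 1 = 1.5 x ULN. Visit summaries show how the group moves; they do not show the distribution of individual changes or give an interval for the mean change.
3. What the addition would provide. The 95% half-width for a mean paired change is t(0.975, n-1)/sqrt(n), in units of the SD of change. For n = 20, the minimum enrolment in Section III, this is 2.093/4.472 = 0.47. For n = 16 (assumed, if four patients lack paired values) it is 2.131/4 = 0.53.

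**The case against.** The strongest reply is that nothing is lost. Item 3 does not say that later events are excluded, item 4 has no time window, and Section VII requires events to be recorded and their incidence reported across the trial. A sensible analyst would include post-treatment events. This stands as a limit on severity: a reader might infer that post-treatment safety data will be lost, and the documents do not support that. What remains is that the sentence defining the analysis names a narrower period than the sections it should serve, and the plan should not depend on the analyst disregarding it.

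A reader might also infer that two thirds of the safety information goes unanalysed. That does not follow either. The 67% is calendar time at the shortest permitted treatment, falls with longer treatment, and says nothing about how many events occur after stopping.

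On laboratory values, a tempting reading is that the scheduled safety tests have no analysis at all. Sections VII.A and VII.E and the general rule in Section VIII.A contradict it. Nor can it be said that recovery would go unseen: laboratory events are followed back to baseline, and visit summaries would show group-level recovery in the rest. In a descriptive plan, listing within-patient change for the remaining values is closer to a preference about detail than to a defect. I accept that, and put it forward only as a secondary addition.

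**Conclusion.** The period conflict holds. Item 3 of Section VIII.B is narrower than Sections VI.C and VII, and followed literally it would leave post-treatment events out of the analysis of Objective 1. The consequence is conditional on that literal reading, since the events are recorded and reportable under Section VII. The number affected is unknown; the period concerned is 12 months per patient, on the reading that the visits are counted from the end of therapy. The severity is minor.

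The laboratory part holds only for within-patient changes not recorded as adverse events, and excludes haemoglobin, D-dimer and albumin. It is a useful addition because baseline is the sole comparator and entry permits raised liver and kidney values, but it should not carry the weight of the first part.

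**What to change.** Reword item 3 of Section VIII.B along these lines: *Adverse events and side effects will be assessed during medication and through 12 months after treatment, and reported separately for the two periods.* Assign each event to a period by its onset relative to the last dose; the time of each event is already recorded.

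As a secondary addition, list in Section VIII.B a summary of each patient's change from baseline, with 95% intervals, for the scheduled liver, kidney and lipid values and for blood counts other than haemoglobin, at months 3 and 6, end of therapy, and 6 and 12 months after treatment. Say that these summaries supplement the reporting of abnormal laboratory tests as adverse events and do not replace it.

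The cost is one reworded sentence and a few descriptive tables. All the tests are already scheduled, so no extra visits or patients are needed. If AST, ALT, bilirubin and creatinine are shown as multiples of ULN, to match the entry criteria, the laboratory's ULN must be recorded with each result.
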